6.9.3 Bringing costs and outcomes together

The type and extent of economic evaluation will crucially depend upon the clinical outcome of the trial [57]:

- 1. If the rehabilitation outcome is at least the same as usual care, the preferred option will be that which is less costly (which will then depend on whether any reduced further health care use in the rehabilitation group offsets the costs of the programme);
- 2. If rehabilitation is more effective and more costly, the incremental extra cost per quality adjusted life year (QALY) gained will be estimated to aid a decision about whether the additional effectiveness gained from rehabilitation is worthwhile.

Estimation of QALYs is made possible by collection of EQ-5D and SF-36 data within the trial. The EQ-5D is a generic, preference-based measure of quality of life in which 'health' is defined in terms of five broad dimensions. In the UK, patients' assessments of their health states in the EQ-5D classification can be allocated scores derived from a survey of values by members of the general public (where 0=death and 1=full health) [58]. SF-36 has eight dimensions and is similarly scored to the EQ-5D to estimate QALYs. As this is a pilot, the above analysis will be conducted within-trial,

although we will also assess the feasibility on longer-term (lifetime horizon) modelling based on the literature on potential reduced-mortality benefits from such programmes.

7. DISSEMINATION AND PROJECTED OUTPUTS

7.1 Dissemination

The main academic outputs from our research will comprise papers in peer review journals (e.g. study design published in Trials and results published in Supportive Care in Cancer) and oral presentations at national (e.g. National Cancer Research Institute Annual Conference) and international (e.g. World Cancer Congress) conferences. To ensure that the findings from our research impact on the management of health services, knowledge mobilisation will be promoted by the production of short and concise briefings about the research and disseminated to individuals responsible for national cancer strategies (e.g. Cancer Tsar for England and Chair of the Scottish Cancer Task Force). In addition, applicants' networks (involving a range of lay, expert and voluntary sector) will be used to promote knowledge mobilisation so that the findings improve service delivery in the NHS and voluntary sector. Applicants currently hold key positions in local, national and international cancer management, policy and research organisations. [name], [name] and [name] are nurse consultants in NHs Boards and clinical leads for cancer rehabilitation; [name] is physical activity consultant for Macmillan Cancer Support; [name] chairs the lifestyle and behaviour change subgroup of the Psychosocial Oncology National Cancer Research Institute Clinical Studies Group and is a member of EUROCHIP (a European initiative to set quality indicators for cancer rehabilitation); [name] is a member of the colorectal cancer National Cancer Research Institute Clinical Studies Group. Results of the study will also be reported to the Funder and will be available on their web site. A lay summary for patient study participants and a summary for health professionals will also be produced. To complement this activity, we will aim to publicise the study and its findings through University and study web pages, NIHR HS&DR website and appropriate forms of social media such as twitter.

7.2 Outputs

The production of a manual for the rehabilitation intervention will enable us to provide specific guidance on the training and infrastructure that would be needed and the nature of the intervention for a large scale trial. A report of the findings on acceptability and feasibility of the intervention and trial procedures will inform the design of a future large scale trial. An output of the current application will be a subsequent application for an NIHR programme grant, the aim of which will be to develop and evaluate a cost effective and sustainable model of rehabilitation for people affected by cancer. We expect the impact of this research on current practices within the health services community to be high for the following reasons. The demand for cancer rehabilitation is rising due to increasing incidence and survival. This is coupled with growing recognition for the need of rehabilitation to either deal with the late effects of treatment or the physical effects of the disease. Yet, rehabilitation is not strongly articulated in commissioning and this is partly due to lack of knowledge and evidence of what is an acceptable, effective and efficient rehabilitation model for cancer patients. The main attraction of this study is that it is testing the use of an existing and well-established rehabilitation service (i.e. cardiac rehabilitation) for use with another group of patients (i.e. cancer patients). Thus, if implemented it will not require setting up a whole new service for cancer patients. Rather, referral pathways could be easily adapted to ensure that the model is integrated into existing cancer service frameworks with additional resource to accommodate additional patients.

8. PLAN OF INVESTIGATIONS AND TIMETABLE																									
Key stages, milestones and outputs	-	-	-	-	1	2	3	4	5	6	7	8	9	10	11	12	13	14	15	16	17	18	19	20	21
NHS Ethics and R&D approvals (i.e. before study starts)																									
Prepare all study materials (e.g. information sheets forms and logs)																									
Appointment of Research Fellows																									
1 st Steering group meeting																									
PHASE 1																									
Cancer-exercise training for cardiac physiotherapists & evaluation forms																									
completed																									ŀ
Cancer clinicians, recruit and refer 12 cancer patients for rehabilitation																									
Researcher completes screening and recruitment logs																									
Researcher administers questionnaires and accelerometer																									
Patients attend rehabilitation (intervention)																									ŀ
Researcher telephones cancer patients and completes intervention logs																									
Researchers conducts interviews with 12 cancer patients																									
Researcher recruits 6 cardiac patients and conduct interviews																									
Researcher recruits 6 clinicians and conduct interviews																									
Researcher and Tayside CTU conducts analysis and prepares report																									
2 nd steering group meeting																									
Investigators use Phase 1 report to prepare for Phase 2																									
PHASE 2																									
Cancer clinicians recruit, and refer cancer patients for rehabilitation																									
Researcher completes screening and recruitment logs																									
ı ,	esearcher administers questionnaires and accelerometer (baseline – T0)																								
Tayside CTU randomises participants to intervention or control groups																									
Patients attend rehabilitation (intervention)																									
Researcher telephones cancer patients and completes intervention logs																									
Researcher administers questionnaires and accelerometer (follow up T1)																									
Researcher administers questionnaires and accelerometer (follow up T2)																									
Researcher conducts 24 interviews with patients & 12 with clinicians																									ŀ
Researcher and Tayside CTU conducts analysis and prepares report	conducts analysis and prepares report																								
3 rd steering group meeting																									
Investigators produce i) manual for the rehabilitation intervention, ii)																									
submit final report, iii) plan for developing larger trial and dissemination																									

9. PROJECT MANAGEMENT

The responsibility for obtaining NHS ethical and local R&D management approval will lie with the Chief Investigator. The Chief Investigator will be responsible for overseeing the progress of the study. The day-to-day management of the feasibility study (Phase 1) will be co-ordinated by the Chief Investigator and the day-to-day management of the pilot RCT (Phase 2) will be co-ordinated by the Trial Manager located at the Tayside Clinical Trials Unit. Responsibility for day-to-day line management of appointed researchers will be the Chief Investigator during Phase 1 and the Tayside Clinical Trials Unit Trials Manager for Phase 2. Tayside Clinical Trials Unit will be responsible for maintaining and archival of study documentation. The Chief Investigator and Trial Manager will take responsibility for ensuring that the study abides by the policies of the Research Governance Framework for Health and Community Care (Scotland), the Data Protection Act and any other relevant legislation and regulatory guidance. All co-Investigators will assist the Chief Investigator and carry out designated tasks in accordance with the study protocol. A study steering group will be responsible for advising the Chief Investigator and Trial Manager about the study. It will meet on three occasions: at the commencement of the study, at the end of Phase 1 and at the end of Phase 2 to provide advice and guidance. This group includes the Chief and co-Investigators, a representative from colorectal cancer and cardiac rehabilitation clinical teams and two patient representatives and Operations Manager (Scotland) from Bowel Cancer UK. Site specific local Investigators are co-investigators ([name], [name] and [name]) and will be responsible for ensuring that all trial-related clinical decisions (e.g. screening for contraindications to exercise) are made and that the recruitment strategy is implemented and the research conducted in their site complies with local NHS ethics and research governance.

10. APPROVAL BY ETHICS COMMITTEE

10.1 Ethics and R&D approvals and guidance

NHS ethical approval and local R&D management approvals will be obtained before the study starts and this has been made clear in the project timetable.

10.2 Risks to participants

This is a low risk study and major risks and safety issues are not anticipated. No invasive procedures are being used in this study. The intervention includes an exercise component during the period of recovery following surgery. Moderate physical activity is recommended for colorectal cancer patients during treatment and has no contraindications for most [49]. The American College of Sports Medicine recommend that cancer patients avoid inactivity and return to normal activity as soon as possible after diagnosis and treatment and should engage in at least 150 minutes per week of moderate intensity or 75 minutes per week of vigorous intensity aerobic physical activity, or an equivalent combination of moderate and vigorous intensity aerobic physical activity [59]. Evidence suggests that it is not only feasible to exercise during the period of recovery post-surgery but that it can improve cardiovascular fitness, muscle strength, body composition, fatigue, anxiety, depression, self-esteem, and quality of life [49]. Nevertheless, effects of treatment may increase the risk of exercise-related injuries and adverse effects and so during the screening process for study participation those patients who are contraindicated for moderate intensity physical activity or who have an injury or illness which might be aggravated by exercise, will be excluded from the study:

- 1. The patient's cancer clinical team at a post-treatment follow up appointment will assess if there are contraindications to exercise due to cancer and late effects of treatment (e.g. patients with severe anaemia or with compromised immune function).
- 2. A cardiac rehabilitation clinician (e.g. cardiac nurse/cardiac physiotherapist) will conduct a clinical/risk stratification assessment to determine whether a patient can safely exercise from a cardiac clinical perspective.
- 3. During rehabilitation the cardiac physiotherapist running the exercise class will monitor patients for adverse events (e.g. chest pain, extreme breathlessness) and will decide whether it is safe for the patient to continue participation. An adverse events log will be kept for the duration of the study.
- 4. Patients will be advised and encouraged to contact their colorectal cancer Clinical Nurse Specialist if they have any questions or concerns about their health during the trial.

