6.7.4 Intervention and control

Participants will either receive rehabilitation (intervention group) or a 'Staying healthy after bowel cancer' booklet by Bowel Cancer UK (control group), as described in Section 6.4 above. However, we may make slight modifications to the intervention based on the findings of the feasibility study, which will be documented. To optimise intervention fidelity [53], interventionists will be expected to follow the cancer patient rehabilitation pathway (see Appendix 1) for this study and their site-specific rehabilitation programme. To meet Objectives 6 and 9, a researcher will contact participants randomised to the rehabilitation group each week by telephone in order to complete an intervention record log to document for example, type and duration of exercises completed and content of educational classes attended for participants receiving the intervention. A researcher will also contact participants randomised to the control group to record for example, any advice given about exercising.

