6.7.7 Adverse event reporting

Although this is not a Clinical Trial of an Investigational Medicinal Product, the Investigators will adhere to Tayside Medical Science Centre (TASC) SOP 11, 'Identifying recording and reporting adverse events for clinical trials of investigational medicinal products' with expedited reporting to the Sponsor as required. This will be overseen by Tayside Clinical Trials Unit.

In particular the following Serious Adverse Event (SAE) will be reported within 24 hours of the PI or person delegated responsibility for recording SAEs becoming aware of them:

(SAE): any adverse event occurring that results in any of the following outcomes:

- Death:
- In-patient hospitalization or prolongation of existing hospitalization;
- Persistent or significant disability/incapacity;

The following protocol exclusions will apply: -

- Hospitalisation for assault or accidental injury
- Hospitalisation for pre-planned surgery

The above protocol exclusions will be recorded in the Adverse Event (AE) log for the trial and line listings will be reported annually to ethics and the Sponsor.

Note: Medical and scientific judgment should be exercised in deciding whether expedited reporting is also appropriate in situations other than those listed above. For example, important medical events may not be immediately life threatening or result in death or hospitalization but may jeopardize the subject or may require intervention to prevent one of the outcomes listed in the definition above. Any adverse event is considered a serious adverse event if it is associated with clinical signs or symptoms judged by the investigator to have a significant clinical impact.

It is also worth noting that each hospital and hence cardiac rehabilitation programme will have a reporting system for adverse events (e.g. Datix) and cardiac rehabilitation programme operate incident reporting.

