6.9.2 Further impacts on health care use

At each assessment with patients in both rehabilitation and usual care groups, we will ask them to report on: general practitioner visits; hospital emergency department visits and hospital admissions; visits to allied health departments such as physiotherapy and occupational therapy, nutrition, social work and vocational rehabilitation. Patients will also be asked to report on any medications used. A schedule of relevant items will be constructed about which we will ask questions on frequency of use in the previous three months (to match times of regular follow-up proposed in the main trial. Data on hospital visits and drug use will also be available through NHS records. The above items will be costed at NHS pay and prices or, where appropriate, using other (e.g. market-based) sources. Data on rehabilitation programme costs and those on further impacts will be aggregated and the statistical significance of differences in cost per patient between intervention and control group assessed by appropriate methods depending on the distributional characteristics of the data.

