## **Summary of Study Data**

All continuous variables will be summarised using the following descriptive statistics: n (non-missing sample size), number of missing records, mean, standard deviation, median, maximum and minimum. The frequency and percentages (based on the non-missing sample size) of observed levels will be reported for all categorical measures. In general, all data will be listed, sorted by subject and treatment and where appropriate by visit number within subject.

All summary tables will be structured with a column for each treatment in the order (Intervention, Control) and an additional column for the total population relevant to that table/treatment, including any missing observations'

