## **Safety Analyses**

### **Adverse Events**

Adverse events (AE) will be coded with MedDRA 16.1. Where more than one diagnosis is present in the AE description, the AE will be split with all the descriptors kept the same for all diagnosis. Adverse events will be reported by primary System Organ Class (SOC) and Preferred Term (PT).

Subjects will be counted only once when calculating the incidence of AEs. An overview table will be created counting the number of adverse events by system organ class and preferred term.

Descriptors for Adverse events will be tabulated separately as described for categorical variables in section 8. The total number of AEs will be used as basis for tabulation.

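### Active adverse event monitoring during follow-up is specified only in the exercise classes, with no equivalent enquiry for controls, so by-arm tables of non-serious events are at risk of ascertainment bias

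*Protocol*

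**What the plan says.** **Detection in the rehabilitation arm.** Protocol 10.2, item 3: "During rehabilitation the cardiac physiotherapist running the exercise class will monitor patients for adverse events". Items 1 and 2 of that list are safety checks before entry, not follow-up. Protocol 6.7.4 adds that "a researcher will contact participants randomised to the rehabilitation group each week by telephone" to complete a log of, for example, exercise done and education attended. Protocol 6.7.7 notes that "each hospital and hence cardiac rehabilitation programme will have a reporting system for adverse events"; the programme's own system can only see people who attend it.

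**Detection in the control arm.** Controls receive a booklet and attend no class (Protocol 6.4). On contact, 6.7.4 says: "A researcher will also contact participants randomised to the control group to record for example, any advice given about exercising". It gives no frequency, and its one example is not an adverse event.

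**Routes open to both arms.** Protocol 10.2: "An adverse events log will be kept for the duration of the study". Patients are also encouraged to ring their cancer nurse specialist with concerns. Protocol 6.7.7 applies a trials-unit procedure for identifying, recording and reporting adverse events, and requires serious events to be reported within 24 hours of staff becoming aware of them. At each assessment, patients in both arms are questioned about health care use in the previous three months (Protocol 6.9.2): "we will ask them to report on: general practitioner visits; hospital emergency department visits and hospital admissions". The same section says hospital data will also be available from NHS records.

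**Reporting.** SAP, Summary of Study Data: "All summary tables will be structured with a column for each treatment in the order (Intervention, Control", plus a total column. SAP, Adverse Events, groups events by MedDRA class and term, counts each subject once for incidence, and says of event descriptors: "The total number of AEs will be used as basis for tabulation". Serious events are reported with all the others and reviewed case by case by the principal investigator. SAP, Secondary Efficacy Analyses, leaves service use to the health economics team. No test of adverse events is stated, and no caveat on how events were found.

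**The concern.** A count of recorded events is the product of how often events happen and how often someone notices them. Here the second factor may differ by arm because of the plan itself. A breathless or injured patient in class is seen by a clinician told to watch for such things, and that patient also speaks to a researcher every week. A control with the same problem is recorded only if the patient volunteers it or a contact of unspecified frequency happens to bring it out. The trial is open label (SAP, Randomisation and Blinding), so nothing offsets this.

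Readers of the report will see two columns and compare them, whether or not a test is attached. An excess in the rehabilitation column could be real harm from exercise or simply closer watching, and the table could not separate the two. This matters beyond the pilot, because one of its aims is to refine procedures for a definitive trial (Protocol 5). An unequal method of collecting harms could be carried forward. Protocol 10.2 itself accepts that effects of treatment may raise the risk of exercise-related injury, so this is a comparison readers will want.

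**Working it through.** The documents give no adverse event rate, no capture rate and no harm comparison, so there is no figure of the plan's to reproduce. The check has two parts.

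**1. Sources of events by arm, from the text**

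| Source | Rehabilitation | Control | Finds unreported events? | Linked to the adverse event log? |
|---|---|---|---|---|
| Physiotherapist in class (10.2) | Yes | No | Yes | Implied |
| Rehabilitation programme incident reporting (6.7.7) | Yes | No | In class only | Not stated |
| Researcher calls (6.7.4) | Weekly | Frequency not stated | Only if asked; no such question stated | Not stated |
| Patient contacts cancer nurse (10.2) | Yes | Yes | No, patient-initiated | Not stated |
| 24-hour serious event rule (6.7.7) | Yes | Yes | No, starts at awareness | Yes |
| Admissions and emergency visits at each assessment (6.9.2) | Yes | Yes | Yes, hospital events | Not stated |
| NHS records (6.9.2) | Yes | Yes | Yes, hospital events | Not stated |

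The sources that could find non-serious events without the patient volunteering them sit in the rehabilitation arm. The sources that treat the arms alike mainly cover hospital events.

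**2. What unequal capture would do to the table (illustration)**

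Arm size: 13 + 13 + 7 = 33 (Protocol 6.2.3). Assume the same true proportion p of patients with an event in each arm, and capture probabilities c_R (rehabilitation) and c_C (control). Then:

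- observed proportion = p × c
- expected patients with a recorded event = 33 × p × c
- apparent risk ratio = c_R / c_C, which does not depend on p
- spurious difference = p × (c_R − c_C)

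Risk ratios: 0.90 / 0.70 = 1.29 and 0.90 / 0.50 = 1.80.

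| p | Capture R v C | Expected patients R v C | Spurious difference | Chance R count exceeds C count |
|---|---|---|---|---|
| 20% | 90% v 90% | 5.9 v 5.9 | 0 points | 0.44 |
| 20% | 90% v 70% | 5.9 v 4.6 | 4 points | 0.61 |
| 20% | 90% v 50% | 5.9 v 3.3 | 8 points | 0.78 |
| 30% | 90% v 70% | 8.9 v 6.9 | 6 points | 0.67 |
| 30% | 90% v 50% | 8.9 v 5.0 | 12 points | 0.86 |

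The last column compares two independent exact binomial counts. For p from 10% to 40%, the spurious difference runs from 2 to 8 points at 90% v 70%, and from 4 to 16 points at 90% v 50%. With equal capture of 90% the difference is zero, and the chance that the rehabilitation count is the higher is 0.41 to 0.45. All values of p and c are assumptions.

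**The case against.** The case on the other side has real force.

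- **Controls are not without a route.** The log runs for the whole study, nurse contact is open to all, and the trials-unit procedure is not limited to one arm. Its content is not in the documents and may include systematic enquiry. This stands: the point can only concern what the protocol and SAP state.
- **The call contents are examples.** Protocol 6.7.4 lists them with the words for example, and the case report forms are not available. A reader might infer that the calls carry no adverse event item, or that controls are called less often. The text shows neither. It shows only that no such item, and no control schedule, is specified.
- **Serious events are better covered.** A reader might infer that control admissions, or those after classes end, escape serious event reporting. That is not supported. The three-month recall period at T2 covers the three months since T1, NHS records are a further source, and the 24-hour clock starts at awareness, so an admission disclosed at an assessment could still be reported, though late. What remains is that no text carries these data into the log.
- **The SAP already counts each subject once for incidence**, and the principal investigator reviews each serious event. Both stand and should be kept. A reader might also infer that basing descriptors on total events will make the more closely watched arm look less serious. That requires seriousness to be one of the tabulated descriptors, which the SAP does not say.
- **No harm test is planned and safety is not among the objectives.** True, and it limits the consequence. Counts of 9 v 5 out of 33 give a Fisher p-value of 0.37, so a careful reader would infer little. Descriptive columns are still compared, and they may inform the next trial.

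**Conclusion.** The concern holds as a risk to the by-arm tables of non-serious adverse events, with under-counting in controls the likelier direction. It does not hold as a statement that the comparison is biased or that control events are missed: the documents give no capture rates and the procedure they rely on is not available. Nor does it follow that the pilot's safety data would be useless, since class-observed events and individually reviewed serious events remain informative. Hospital admissions and deaths are less exposed, subject to the missing link between health care use data and the log.

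The size is unknown. Apparent risk ratios of 1.3 to 1.8 with no true difference follow from assumed capture of 90% in the rehabilitation arm and 70% to 50% in controls. Confidence is moderate.

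**What to change.** 1. **Collection (Protocol 6.7.4, 6.7.5, 10.2).** Ask both arms the same fixed question, covering any new illness, injury, emergency visit or admission since last contact, at T1, at T2 and at telephone contacts made on the same schedule in both arms. The SAP describes conduct in the past tense, so this applies only where contacts are still to come.
2. **Reconciliation (Protocol 6.9.2 and 6.7.7).** Check admissions and emergency visits from the health care use questions and NHS records against the adverse event and serious event log, in both arms. This may remain possible after the contacts are complete.
3. **SAP, Safety Analyses.** Record how each event was detected. Keep the planned patient-level incidence, and add the number and percentage of randomised patients with at least one serious event by arm, using sources common to both arms. List class-observed events separately, without comparison. State that non-serious events may have been detected unequally.

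Cost: slightly longer contacts, more events to log and code, one reconciliation check, and a few lines of protocol and SAP text. In-class monitoring itself is left unchanged.
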